#### 6.1.2.6 Postoperative Therapy, Day 1 of Each Cycle

Following CN/MET, continuation of pembrolizumab-based therapy for patients who achieved pre-operative CR/PR/SD will proceed as follows:

- Subjects with an R0 resection (NED, margins negative) or R1 resection (microscopic disease, margins positive) will continue receiving their assigned pembrolizumab-based combination therapy for up to 9 cycles or until disease progression, death, unacceptable toxicity, or withdrawal of consent, whichever occurs first
- Subjects with an R2 resection (macroscopic disease after surgery), or who had a pre-operative CR but did not undergo CN, will continue receiving their assigned pembrolizumab-based combination therapy for up to 18 cycles or until disease progression, death, unacceptable toxicity, or withdrawal of consent, whichever occurs first.
- Subjects may resume therapy following CN/MET as soon as 21 days following surgery (subjects with metastatic disease who have a CR during the preoperative period and therefore do not undergo MET will have no interruption in their therapy). Prior to resuming therapy, the subject must be evaluated by their surgeon and appropriate wound healing must be documented. Subjects with wound healing complications that have not resolved with 42 days of CN and/or MET will discontinue study participation. Any subject who

cannot resume study therapy within 42 days of CN/MET will discontinue study participation.

Perform the following study procedures on Day 1 of each cycle ( $\pm 3$  days) unless stated otherwise:

- Directed physical examination
- Vital signs and weight
- ECOG performance status
- Evaluation of AEs
- Concomitant medications
- CBC with differential and platelet count
- Blood chemistry assessment, including:
  - ALP, ALT/AST, total bilirubin, calcium, phosphorus, BUN, creatinine, total protein, albumin, fasting glucose, potassium, sodium, chloride, bicarbonate, uric acid, LDH
- Thyroid Function Tests: TSH, FT4, T3
- Blood for correlative studies (including immune monitoring) at week 15 only
- Urinalysis (including microscopic exam, if abnormal results are noted)
- Treatment:
  - All cohorts, metastatic disease and achieved CR:
    - Pembrolizumab 400 mg IV (Day 1) Q6W
  - Cohort A (all other subjects continuing therapy):
    - Pembrolizumab 400 mg IV (Day 1) Q6W
  - Cohort B (all other subjects continuing therapy):
    - Pembrolizumab 400 mg IV (Day 1) Q6W
    - Axitinib (Days 1 - 42). Dose titration per standard of care
- Imaging evaluation (CT chest, abdomen and pelvis; MRI if CT is contraindicated; IV contrast given unless contraindicated; Bone scan if clinical indicated; MRI brain if clinically indicated) for tumor assessment will be performed every 2 cycles (as indicated in study flow chart [Section 6.2])

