- Subjects with PD during the preoperative treatment period who, in the opinion of the treating physician and principal investigator, are likely to benefit from CN/MET AND in whom surgery is safe and feasible, may proceed with CN/MET on study. Subjects in whom CN/MET is unlikely to provide benefit OR surgery is not safe and feasible, may proceed with tumor biopsy on study, if safe and feasible. Subjects will withdraw from study participation following CN/MET or tumor biopsy. If CN/MET and tumor biopsy are not safe and feasible and not in the best interests of the subject, the subject will withdraw from study participation immediately. The risk of disease progression during the preoperative treatment period is 10% [18]. The use of anti-PD-1 antibodies has now become standard of care. As a result, participants are receiving treatment that is deemed standard of care.
- Subjects with PR/SD in whom CN/MET is not safe and feasible: in rare cases, subjects who were deemed eligible for CN/MET prior to study participation and have PR/SD to preoperative therapy may not be able to undergo CN/MET (for example, due to adverse events). These subjects will be required to provide a tumor biopsy, unless deemed unsafe or delays appropriate standard of care, in lieu of CN/MET. Subjects may continue study treatment with pembrolizumab 400 mg Q6W for up to 1 year (9 cycles), or until disease progression, death, unacceptable toxicity, or withdrawal of consent, whichever occurs first. The chance of experiencing severe toxicities related to study drug(s) that might preclude or delay surgery is less than 5%.

Following CN/MET, post-operative therapy for patients who achieved pre-operative CR/PR/SD will proceed as follows:

- Subjects with an R0 resection (NED, margins negative) or R1 resection (microscopic disease, margins positive) will continue receiving their assigned pembrolizumab-based combination therapy (with pembrolizumab dosing as 400 mg Q6W) for up to 9 cycles or until disease progression, death, unacceptable toxicity, or withdrawal of consent, whichever occurs first.
- Subjects with an R2 resection (macroscopic disease after surgery), or who had a pre-operative CR but did not undergo CN, will continue receiving their assigned pembrolizumab-based combination therapy (with pembrolizumab dosing as 400 mg Q6W) for up to 18 cycles or until disease progression, death, unacceptable toxicity, or withdrawal of consent, whichever occurs first.

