#### **Post-CN/MET treatment:**

Following CN/MET (or continued therapy in metastatic subjects who achieve CR during the preoperative treatment period), subjects will be offered the option to continue treatment on study as summarized in Section 3.1 (see Section 6.3 for exceptions).

The first dose of post-CN/MET therapy will be no sooner than 21 days, and no later than 42 days, following CN/MET, based on adequate postoperative recovery (including wound healing), as assessed by the treating physicians. Subjects with metastatic disease who achieve CR during the preoperative treatment period (obviating the need for metastasectomy) will continue with their pembrolizumab-based therapy without a break allowing for surgery and recovery. Subjects will receive pembrolizumab 400 mg Q6W, administered on Day 1 of each 42-day cycle.

- In subjects who continue on the combination of pembrolizumab and axitinib as continued therapy following CN/MET (or following CR during preoperative therapy in metastatic patients), axitinib dose-titration (as well as dose modification and delays) should be managed by the treating physician per standard of care.

- Subjects treated with the combination of pembrolizumab and axitinib may experience AEs attributable to axitinib that require holding or discontinuing axitinib. Dose delays or discontinuation of axitinib should be managed per standard of care. In cases where axitinib must be discontinued permanently due to toxicity, subjects may remain on study and receive pembrolizumab monotherapy. In cases where axitinib is held due to toxicity:
  - Subjects who resume axitinib within 42 days may continue to receive combination therapy
  - Subjects who do not resume axitinib within 42 days may remain on study and receive pembrolizumab monotherapy (400 mg Q6W), and axitinib must be discontinued for the remainder of the study duration
  - Subjects treated with the combination of pembrolizumab and axitinib may also experience AEs attributable to pembrolizumab that require holding or discontinuing pembrolizumab. Dose delays, modifications, and discontinuations are discussed in Section 5.2. In cases where pembrolizumab must be discontinued due to toxicity, subjects may remain on study and receive axitinib monotherapy. In cases where pembrolizumab is held due to toxicity:

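### Cohort B subjects with metastatic disease and a preoperative CR are given pembrolizumab alone in the 6.1.2.6 treatment list, but their assigned combination in 3.1 and 5.1.2.2

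*Combined protocol and SAP*

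**What the plan says.** Section 6.1.2.6 ends with a treatment list in three parts:

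- The first, "All cohorts, metastatic disease and achieved CR", contains pembrolizumab 400 mg every 6 weeks and nothing else.
- The second is Cohort A, limited to all other subjects continuing therapy. It also contains pembrolizumab alone.
- The third is "Cohort B (all other subjects continuing therapy". It contains pembrolizumab and the only axitinib entry in the list: "Axitinib (Days 1 - 42). Dose titration per standard of care".

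The opening bullets of the same section say that a subject "who had a pre-operative CR but did not undergo CN, will continue receiving their assigned pembrolizumab-based combination therapy", for up to 18 cycles. Section 3.1 gives the same rule in nearly the same words.

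The Cohort B plan (5.1.2.2, under the post-CN/MET heading) says: "Subjects with metastatic disease who achieve CR during the preoperative treatment period (obviating the need for metastasectomy) will continue with their pembrolizumab-based therapy". It then addresses axitinib for subjects on the combination, after surgery "or following CR during preoperative therapy in metastatic patients), axitinib dose-titration (as well as dose modification and delays) should be managed by the treating physician".

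**The concern.** Section 6.1.2.6 is the visit-by-visit section that site staff and pharmacy would work from on Day 1 of each cycle. Someone following its treatment list would not dispense axitinib to a Cohort B subject with metastatic disease and a CR. Someone following 3.1, or the top of 6.1.2.6, would. Either course could be recorded as a protocol deviation against the other text.

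For the analysis, subjects with CR are named in the DFS group for continued therapy (sections 2.2.2 and 8.1). No rule separates that group by the regimen received. If the two readings are both applied, or only the treatment list is applied, Cohort B's DFS describes a mixture of combination and pembrolizumab alone, and membership of the second group is determined by having responded best.

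**Working it through.** No figure in the plan has to be reproduced here; the check is a comparison of texts. The question put to each is what a Cohort B subject with metastatic disease and a preoperative CR receives after the preoperative period.

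| Place | Regimen for this subject |
|---|---|
| 6.1.2.6, treatment list | Pembrolizumab only |
| 6.1.2.6, opening bullets | Assigned combination, up to 18 cycles if no CN |
| 3.1 | Assigned combination, up to 18 cycles if no CN |
| 5.1.2.2 | Continues on-study treatment as set out in 3.1; axitinib titration guidance covers metastatic CR |
| 5.1.4 | Combination; no exception for CR |
| Table 4 | Axitinib on Days 1–42 for Cohort B; no exception for CR |
| Table 7 and footnote r | Axitinib marked at every postoperative treatment visit for Cohort B; assigned therapy for CR without CN |

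**Can the first line of the list be a backbone common to all cohorts?** No. The Cohort A and Cohort B lines that follow each repeat pembrolizumab and are each restricted to all other subjects. The three lines are mutually exclusive, so a subject on the first line is not also on the Cohort B line.

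**Does the different trigger in 3.1 remove the conflict?** Section 3.1 and the opening bullets turn on not having undergone CN, whereas the treatment list turns on metastatic disease. A metastatic subject with a CR who has no CN falls under the 18-cycle rule with the assigned combination. One who has surgery with an R0 or R1 resection falls under the 9-cycle rule, also with the assigned combination. Neither route through 3.1 leads to pembrolizumab alone.

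**Is CR given elsewhere as a reason to stop axitinib?** No. Section 5.1.2.2 describes a move to pembrolizumab alone only when axitinib is stopped for toxicity or is held and not resumed within 42 days.

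**Number affected.** The documents give no rate of CR after 9 weeks for metastatic subjects on this combination, so a range is assumed.

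- Cohort size without dose reduction (8.2.1): 30.
- Assumed share with metastatic disease and CR at week 10: 0–10%.
- 0 × 30 = 0; 0.10 × 30 = 3. Hence 0 to 3 subjects.
- Maximum treatment per subject: 18 × 42 days = 756 days.

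**The case against.** The strongest reply is that the treatment list is a lone outlier. Section 3.1, section 5.1.4, both tables and the opening bullets of 6.1.2.6 state no pembrolizumab-alone rule for CR, so the practical ambiguity may be small. It can be added that 5.1.2.2 is conditional: its axitinib guidance applies to those who do continue the combination, and its sentence on metastatic CR says only that they stay on pembrolizumab-based therapy.

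The imbalance is real, but it does not tell staff to disregard an explicit line in the procedures section, and it does not establish which text was intended. The point about 5.1.2.2 fails. That section sends these subjects to the treatment set out in 3.1, and its axitinib guidance names metastatic CR, a case that cannot arise if the treatment list governs.

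The objections about size carry more weight. Section 5.1.2.2 already allows Cohort B subjects to continue on one drug after toxicity, so the DFS group is not of one regimen in any case; what is new is mixing by response. DFS is reported descriptively (8.4.3), and 8.4.1 calls it exploratory. It is also unclear whether an unresected CR belongs in the DFS group, since 2.2.2 and 8.1 can be read as requiring an R0 resection. The assumed 0–10% has no anchor in the documents, and locally advanced subjects with CR proceed to CN and are outside the treatment-list line.

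**Conclusion.** The contradiction stands: section 6.1.2.6 conflicts with 3.1, with 5.1.2.2 and with its own opening bullet over which drugs a defined group receives. It deserves correction because it concerns treatment given, possibly for up to 756 days per subject. Its statistical effect is modest. The primary endpoint compares baseline and surgical specimens and ORR is assessed before surgery, so neither changes, and no test or boundary depends on DFS. The number affected, 0 to 3 of 30, rests wholly on the assumed 0–10% and may be zero. The effect on Cohort B's DFS also depends on whether unresected CR subjects are counted in it.

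**What to change.** Reconcile the treatment list in 6.1.2.6 with its opening bullets, 3.1, 5.1.2.2 and 5.1.4, so that one postoperative regimen is stated for Cohort B subjects with metastatic disease and a preoperative CR. Bring Table 4, Table 7 and footnote r into line with whatever is stated. Which regimen applies is for the sponsor and investigators to decide; no view is taken here. If any such subject has already been treated, the report of Cohort B's continued-therapy results should state which regimen that subject received. The cost is wording in an amendment; sample size, assessments and the primary analysis are unchanged.

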### 6.1.3 Post-Treatment Period

#### 6.1.3.1 End-of-Treatment

The following study procedures should be completed within 7 days of the last dose of study drug or discontinuation:

- Directed physical examination
- Vital signs and weight
- ECOG performance Status
- Evaluation of AEs
- Concomitant medications
- Urinalysis (including microscopic exam if abnormal results are noted)
- CBC with differential and platelet count
- Blood chemistry assessment, including:
  - ALP, ALT/AST, total bilirubin, calcium, phosphorus, BUN, creatinine, total protein, albumin, fasting glucose, potassium, sodium, chloride, bicarbonate, uric acid, LDH
- Thyroid function tests: TSH, FT4, T3
- Imaging evaluation (CT chest, abdomen and pelvis; MRI if CT is contraindicated; IV contrast given unless contraindicated; Bone scan if clinical indicated; MRI brain if clinically indicated), for tumor assessment. If prior scan was done within 6 weeks, does not have to be repeated (per physician discretion)
- Newly obtained (biopsy) tissue collection (subjects will require additional consent) at the time of disease progression.
- Blood for correlative studies (including immune monitoring)
- Correlative Studies Stool Collection

#### 6.1.3.2 Safety Follow-Up

The mandatory Safety Follow-up Visit should be conducted 30 days (+7 days) after the last dose of study treatment or before initiation of a new anticancer treatment, whichever comes first. All AEs that occur prior to the Safety Follow-up Visit should be recorded. Subjects with an AE of Grade >1 will be followed until the resolution of the AE to Grade 0-1 or until the beginning of a new anticancer therapy, whichever occurs first. Serious AEs (SAEs) that occur within 90 days of the end of treatment or before initiation of a new anticancer treatment should also be followed and recorded.

The following procedures will be performed at the Safety Follow-up Visit:

- Directed physical examination
- Vital signs and weight
- ECOG performance Status
- Evaluation of AEs
- Concomitant medications
- Urinalysis (including microscopic exam if abnormal results are noted)
- CBC with differential and platelet count
- Blood chemistry assessment, including:
  - ALP, ALT/AST, total bilirubin, calcium, phosphorus, BUN, creatinine, total protein, albumin, fasting glucose, potassium, sodium, chloride, bicarbonate, uric acid, LDH
- Thyroid function tests: TSH, FT4, T3

#### **6.1.3.3 1-Year Follow-Up**

Those subjects who complete preoperative therapy and achieve either CR/PR/SD with R0 or R1 resection, and complete 1 year (9 cycles) of continued pembrolizumab-based therapy will be followed for up to 1 additional year (12 months), or until disease progression, death, unacceptable toxicity or withdrawal of consent, whichever occurs first.

Those subjects who complete preoperative therapy and achieve either CR/PR/SD with R2 resection, or achieve a pre-operative CR but do not undergo CN, and complete 2 years (18 cycles) of continued pembrolizumab-based therapy (400 mg Q6W) will be followed for up to 12 additional months, or until disease progression, death, unacceptable toxicity or withdrawal of consent, whichever occurs first.

During the 1-year follow-up period, the following procedures will be performed every 12 weeks(±14 days) from the date of last dose of study treatment or discontinuation:

- Directed physical examination
- Vital signs and weight
- ECOG performance status
- Evaluation of AEs
- Concomitant medications

- CBC with differential and platelet count
- Blood chemistry assessment, including:
  - ALP, ALT/AST, total bilirubin, calcium, phosphorus, BUN, creatinine, total protein, albumin, fasting glucose, potassium, sodium, chloride, bicarbonate, uric acid, LDH
- Thyroid Function Tests: TSH, FT4, T3
- Urinalysis (including microscopic exam, if abnormal results are noted)
- Imaging evaluation (CT chest, abdomen and pelvis; MRI if CT is contraindicated; IV contrast given unless contraindicated; Bone scan if clinical indicated; MRI brain if clinically indicated) for tumor assessment will be performed as specified in study flow chart [Table 7])

## 6.2 Trial Flow Chart

**Table 7: Schedule of Activities**

Trial Period:	Screening Phase	Preoperative Treatment Period Visit Number				CN/MET	Postoperative Continued Treatment Visit Number f				Post-Treatment		
	Screening	1 (W1)	2 (W4)	3 (W7)	4 (W10)	(W12)	Up to 9 cycles g OR Up to 18 cycles h				END OF TX k	Safety F/U	F/U for subjects who complete 1Y q or 2Y r of continued TX
							5 (W15) v	6 (W21)	7 (W27)	8-40 (W33-125)			
Scheduling Window:	-28d to -1d	D1	D1 ±3d	D1 ±3d	D1 ±3d	+7d	D1 ±3d	D1 ±3d	D1 ±3d	D1 ±3d	At DC w +7d	30d after DC w +7d	Q12W after DC w ±7d, for up to 1Y
Administrative Procedures													
Informed Consent	X												
Inclusion/Exclusion Criteria	X												
Demographics/Medical History and Baseline Conditions Assessment	X												
Prior and Concomitant Medication Review	X o	X	X	X	X	X	X	X	X	X	X	X	X

Trial Period:	Screening Phase	Preoperative Treatment Period Visit Number				CN/MET	Postoperative Continued Treatment Visit Number f				Post-Treatment		
	Screening	1 (W1)	2 (W4)	3 (W7)	4 (W10)	(W12)	Up to 9 cycles g OR Up to 18 cycles r				END OF TX k	Safety F/U	F/U for subjects who complete 1Y q or 2Y r of continued TX
							5 (W15) v	6 (W21)	7 (W27)	8-40 (W33-125)			
Scheduling Window:	-28d to -1d	D1	D1 ±3d	D1 ±3d	D1 ±3d	+7d	D1 ±3d	D1 ±3d	D1 ±3d	D1 ±3d	At DC w +7d	30d after DC w +7d	Q12W after DC w ±7d, for up to 1Y
Clinical Procedures/Assessments													
Review Adverse Events		X	X	X	X	X d	X	X	X	X	X	X	X
Complete Physical Examination	X												
Directed Physical Exam		X	X	X		X	X	X	X	X	X	X	X
Vital Signs, Height s , and Weight	X	X	X	X		X	X	X	X	X	X	X	X
ECOG Performance Status	X a	X	X	X	X	X d	X	X	X	X	X	X	X
Laboratory Procedures/Assessments													
Pregnancy Test – Urine or Serum β-HCG e	X												

Trial Period:	Screening Phase	Preoperative Treatment Period Visit Number				CN/MET	Postoperative Continued Treatment Visit Number f				Post-Treatment		
		1 (W1)	2 (W4)	3 (W7)	4 (W10)		5 (W15) v	6 (W21)	7 (W27)	8-40 (W33-125)	END OF TX k	Safety F/U	F/U for subjects who complete 1Y q or 2Y r of continued TX
	Screening						Up to 9 cycles q OR Up to 18 cycles r						
Scheduling Window:	-28d to -1d	D1	D1 ±3d	D1 ±3d	D1 ±3d	+7d	D1 ±3d	D1 ±3d	D1 ±3d	D1 ±3d	At DC w +7d	30d after DC w +7d	Q12W after DC w ±7d, for up to 1Y
PT/INR and aPTT x	X	X c				X d							
CBC with Differential and Platelet Count x	X	X c	X	X		X d	X	X	X	X	X	X	X
Comprehensive Serum Chemistry Panel b,x	X	X c	X	X		X d	X	X	X	X	X	X	X
Urinalysis n,x	X		X			X d	X		X	X	X	X	X
T3, FT4, and TSH x	X		X			X d	X		X	X	X	X	X
Study Treatment													
Pembrolizumab		X	X	X			X	X	X	X			
Axitinib (Cohort B Only)		X	X	X			X	X	X	X			
CN/MET						X							
Efficacy Measurements													
Tumor Imaging j	X				X		X			X g	X h,i		X h,i

Trial Period:	Screening Phase	Preoperative Treatment Period Visit Number				CN/MET	Postoperative Continued Treatment Visit Number f				Post-Treatment		
	Screening	1 (W1)	2 (W4)	3 (W7)	4 (W10)	(W12)	Up to 9 cycles g OR Up to 18 cycles r				END OF TX k	Safety F/U	F/U for subjects who complete 1Y q or 2Y r of continued TX
							5 (W15) v	6 (W21)	7 (W27)	8-40 (W33-125)			
Scheduling Window:	-28d to -1d	D1	D1 ±3d	D1 ±3d	D1 ±3d	+7d	D1 ±3d	D1 ±3d	D1 ±3d	D1 ±3d	At DC w +7d	30d after DC w +7d	Q12W after DC w ±7d, for up to 1Y
Tumor Biopsies/Archival Tissue Collection/Correlative Studies Blood and Stool													
Archival or Newly Obtained Tissue Collection	X t					X u					X m		
Correlative Studies Blood Collection (including immune monitoring)	X	X	X	X		X	X				X		
Correlative Studies Stool Collection and Questionnaire	X				X						X		

Abbreviations: aPTT = activated partial thromboplastin time; β-HCG = beta human chorionic gonadotropin; CBC = complete blood count; DC = discontinuation; ECOG = Eastern Cooperative Oncology Group; FT4 = free thyroxine; F/U = follow-up; INR = international normalized ratio; PT = prothrombin time; Q12W = every 12 weeks; SD = stable disease; T3 = triiodothyronine; TSH = thyroid stimulating hormone; Tx = treatment; D = day; W = week; Y = year.

- To be done within 7 days of Cycle 1 Day 1
- Includes alkaline phosphatase (ALP), aspartate aminotransferase/alanine aminotransferase (ALT/AST), total bilirubin, calcium, phosphorus, blood urea nitrogen (BUN), creatinine, total protein, albumin, fasting glucose, potassium, sodium, chloride, bicarbonate, uric acid, lactate dehydrogenase (LDH)
- Laboratory evaluations may be omitted if they were already performed within 7 days of Cycle 1, Day 1
- Window for these specific assessments is within the 14 days prior to CN and/or MET
- Women of childbearing potential require a negative urine test within 72 hours prior to the first dose of study treatment. Serum test is only required if urine test is positive or is not evaluable. Additional urine pregnancy testing can be conducted if required by local regulations or clinically indicated.

- f. Administered for up to 1 year (9 cycles) (for patients who undergo CN/MET with R0 or R1 resection), or up to 2 years (18 cycles) (for patients who undergo CN/MET with R2 resection or who had a pre-operative CR but did not undergo CN), or until death, disease progression, unacceptable toxicity, or withdrawal of consent.
- g. To be done every 2 cycles (i.e., about every 3 months) during postoperative pembrolizumab-based treatment
- h. If prior scan was done within 6 weeks, does not have to be repeated (per physician discretion)
- i. Those subjects who undergo CN/MET with R0 or R1 resection who complete 1 year (9 cycles) of postoperative pembrolizumab-based therapy, or those patients who undergo CN/MET with R2 resection or who had a pre-operative CR but did not undergo CN and complete 2 years (18 cycles) of postoperative pembrolizumab-based therapy, will have scans Q12W for up to 12 additional months, or until disease progression, death, unacceptable toxicity or withdrawal of consent, whichever occurs first.
- j. Imaging evaluation (CT chest, abdomen and pelvis; MRI if CT is contraindicated; IV contrast given unless contraindicated; Bone scan if clinically indicated; MRI brain if clinically indicated), for tumor assessment
- k. In subjects who complete postoperative pembrolizumab-based therapy: end of treatment visit will be performed within 7 days of the last dose of study drug or discontinuation
- l. In subjects who complete postoperative pembrolizumab-based therapy: additional safety follow-up visit is not necessary; the follow-up visit will be done during the 12 month follow-up period
- m. At the time of disease progression (subjects will require additional consent)
- n. Urinalysis (including microscopic exam if abnormal results are noted)
- o. Record baseline medications taken within 14 days of Cycle 1 Day 1. For stool correlative analysis, it should be noted if antibiotics were taken within 90 days before the first dose of study drug(s).
- p. To be done within 72 hours prior to the start of study drug
- q. Subjects with an R0 resection (NED, margins negative) or R1 resection (microscopic disease, margins positive) will continue receiving their assigned pembrolizumab-based therapy for up to 9 cycles or until disease progression, death, unacceptable toxicity, or withdrawal of consent, whichever occurs first. They will then enter the 1-Year Follow-Up Period.
- r. Subjects with an R2 resection (macroscopic disease after surgery), or who had a pre-operative CR but did not undergo CN, will continue receiving their assigned pembrolizumab-based therapy for up to 18 cycles or until disease progression, death, unacceptable toxicity, or withdrawal of consent, whichever occurs first. They will then enter the 1-Year Follow-Up Period.
- s. Record height at screening only
- t. Newly obtained tissue will be a fresh biopsy of primary or metastatic lesion at study baseline and must be collected from all enrolled subjects. Archival tissues will be prior tissues from primary or metastatic lesions that were originally obtained prior to study consent (where available).
- u. Subject may be consented for core tumor biopsies if CN and/or MET cannot be performed following preoperative pembrolizumab-based therapy. See section 6.1.2.4 for details.
- v. The first dose of study treatment following CN/MET may be no sooner than 3 weeks and no later than 6 weeks following surgery, to allow for postoperative recovery (adequate wound healing and recovery from any postoperative complications) as assessed by the treating surgeon. Subjects who cannot resume therapy within 42 days for any reason will discontinue study participation
- w. The timing of the End of Treatment, Safety Follow-Up and every 12 week visits during the 1-Year Follow-Up Period is relative to the last dose of study drug dosing or discontinuation.

x. These specific screening laboratory assessments (CBC with Differential and Platelet Count, Comprehensive Serum Chemistry Panel, PT/INR and aPTT, T3, FT4, and TSH, urinalysis) should be performed within 10 days of treatment initiation.

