**Table 4 Adjuvant Treatment Regimen Per Cohort**

Cohort	Drug/Dose	Dose Frequency	Route of Administration	Schedule	Dose Levels
A/B/C	Pembrolizumab 400 mg	Q6W	IV	Day 1 of each 42-day cycle (Q6W)	N/A
B	Axitinib 5 mg titratable	BID	PO	Days 1-42 of each 42-day cycle	DL -2: 1 mg BID DL -1: 3 mg BID DL 1: 5 mg BID

Cohort	Drug/Dose	Dose Frequency	Route of Administration	Schedule	Dose Levels
					DL 2: 7 mg BID DL 3: 10 mg BID
C	TBD (agent to be determined)	TBD	TBD	TBD	TBD

Abbreviations: BID = twice daily; DL = dose level; IV = intravenous; N/A = not applicable; PO = by mouth; Q6W = every 6 weeks; TBD = to be determined.

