### 5.1.4 Continuation of Pembrolizumab-based Therapy Following CN/MET

Following CN/MET, post-operative therapy for patients who achieved pre-operative CR/PR/SD will proceed as follows (see Section 6.3):

- Subjects with an R0 resection (NED, margins negative) or R1 resection (microscopic disease, margins positive) will continue receiving pembrolizumab-based combination therapy (with pembrolizumab dosing as 400 mg Q6W) for up to 9 cycles or until disease progression, death, unacceptable toxicity, or withdrawal of consent, whichever occurs first.

- Subjects with an R2 resection (macroscopic disease after surgery), or who had a pre-operative CR but did not undergo CN, will continue receiving pembrolizumab-based combination therapy (with pembrolizumab dosing as 400 mg Q6W) for up to 18 cycles or until disease progression, death, unacceptable toxicity, or withdrawal of consent, whichever occurs first.
- Subjects will begin their first post-operative treatment no sooner than 21 days and no later than 42 days following CN and/or MET.

All subjects will be consented for optional tissue and blood collection at the time of disease progression.

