#### Secondary endpoints:

- The clinical efficacy of preoperative pembrolizumab-based therapy in subjects with advanced RCC will be assessed by ORR, defined as CR or PR by RECIST 1.1 criteria.
- The clinical efficacy of:
  - Continued pembrolizumab-based therapy will be assessed as follows:
    - In subjects who achieve CR or PR/SD followed by R0 resection: proportion of subjects who remain disease-free at the end of the 1 year continued treatment period (1-year DFS rate), and at 1 year following the end of the continued treatment period (2-year DFS rate), and the median DFS.
    - In subjects who achieve PR/SD with residual disease following CN/MET: proportion of subjects who remain progression-free at the end of the 1 year continued treatment period (1-year PFS rate) and at 1 year following the end of the continued treatment period (2-year PFS rate), and the median PFS.
  - Safety will be assessed and reported using NCI CTCAE version 5.0.
    - Surgical complications using Clavien-Dindo classification (Appendix 3)

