#### **8.4.3 Secondary Analysis (or Analysis of Secondary Endpoints)**

The study will use descriptive statistics to report on the ORR (by RECIST 1.1) following preoperative therapy; DFS/PFS rate at 1-year and 2-years following CN/MET; safety/toxicity of preoperative pembrolizumab-based therapy by NCI CTCAE. Median DFS/PFS following CN/MET will be reported using the Kaplan-Meier estimate.

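### For on-schedule R0/R1 completers the last planned scan falls weeks before the 2-year DFS/PFS time point (Cohorts A and B by Section 8.1, Cohort A by Section 8.4.3), and the two sections use different time origins

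*Combined protocol and SAP*

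**What the plan says.** **Treatment.** Table 7, footnote f, describes postoperative therapy after R0 or R1 resection as "Administered for up to 1 year (9 cycles"); R2 subjects, and those with a preoperative CR and no CN, get up to 18 cycles. Table 4 places pembrolizumab on "Day 1 of each 42-day cycle (Q6W") and, in Cohort B, axitinib on "Days 1-42 of each 42-day cycle". Section 5.1.4 starts postoperative therapy "no sooner than 21 days and no later than 42 days following CN and/or MET".

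**Follow-up.** Completers "will have scans Q12W for up to 12 additional months" (Table 7, footnote i). Section 6.1.3.3 says follow-up procedures "will be performed every 12 weeks(±14 days) from the date of last dose of study treatment or discontinuation". Table 7, footnote w, uses the same anchor, but the table header gives a window of ±7 days instead of ±14.

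**Endpoint.** Section 8.1 takes the second landmark "at 1 year following the end of the continued treatment period (2-year DFS rate"), with parallel wording for PFS. Section 8.4.3 reports the "DFS/PFS rate at 1-year and 2-years following CN/MET".

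**The concern.** A landmark rate needs disease status at or after the landmark. If the last scheduled scan comes earlier, an event-free completer has no planned assessment from which 2-year status can be read. Reported as a proportion, the rate must assume that status. Reported from a Kaplan-Meier curve censored at the last scan, on-schedule nine-cycle completers have all left the risk set, and the curve carries an earlier value forward. Event-free proportions only fall with time, so a value read early can equal or overstate the 2-year rate but not understate it.

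Separately, two sections that count from different days do not define one 2-year rate.

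**Working it through.** **The plan's own figure.** Nine cycles × 42 days = 378 days = 1.03 years, which agrees with the 1-year label when counted to the end of cycle 9. The ninth pembrolizumab dose, however, is on day 8 × 42 = 336 after the first postoperative dose.

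**Last follow-up scan.** Scans every 12 weeks within 12 months fall at weeks 12, 24, 36 and 48; week 60 is outside. Week 48 is day 336 after the anchor.

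**Against Section 8.1, with treatment end and scan clock on the same day.**
- Gap = 365 − 336 = 29 days in both cohorts.
- With the +14-day window: 29 − 14 = 15 days.

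If treatment is instead taken to end with cycle 9 while scans run from the last study-drug day, the landmark is day 378 + 365 = 743 after the first postoperative dose:
- Cohort A: last scan at 336 + 336 = 672, so 71 days short (57 with +14).
- Cohort B on axitinib: last scan at 377 + 336 = 713, so 30 days short (16 with +14).

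**Against Section 8.4.3 (730 days from CN/MET).** Last scan = restart gap (21 to 42 days) + last study-drug day + 336.

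| Group, no dose delays | Last scan, days from CN/MET | Against 730 |
|---|---|---|
| A, 9 cycles, from last pembrolizumab dose | 21 + 336 + 336 = 693 to 42 + 336 + 336 = 714 | 37 to 16 short |
| A, with +7 days (Table 7) | 700 to 721 | 30 to 9 short |
| A, with +14 days (Section 6.1.3.3) | 707 to 728 | 23 to 2 short |
| B, 9 cycles, axitinib to the end | 21 + 377 + 336 = 734 to 42 + 377 + 336 = 755 | 4 to 25 past |
| A, 18 cycles (last dose day 17 × 42 = 714) | 1071 to 1092 | 341 to 362 past |
| B, 18 cycles, axitinib to the end (last drug day 755) | 1112 to 1133 | 382 to 403 past |

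For Cohort A, 12 months of follow-up after the last dose closes at 21 + 336 + 365 = day 722 to 42 + 336 + 365 = day 743 from CN/MET.

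**How far apart the two definitions are.** In days from CN/MET, the Section 8.1 landmark for a nine-cycle subject is 722 to 743 if treatment ends at pembrolizumab dose 9, or 764 to 785 (743 + 21 to 743 + 42) if it ends with cycle 9. Section 8.4.3 uses 730. The definitions therefore differ by −8 to +13 days, or by +34 to +55 days.

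**The case against.** The strongest counter-argument is that this is a matter of weeks on a descriptive endpoint, in part of the trial. Much of it stands.

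- **A reader might infer that the 2-year DFS/PFS rate cannot be observed at all in Cohort A, or in any cohort.** The documents do not support that. The PFS group is subjects with residual disease, which includes R2 subjects on 18 cycles; preoperative CR without CN is also on 18 cycles. Both are scanned about a year or more past 2 years from surgery. Cohort C's agent and schedule are undecided, so nothing can be checked there.
- **A reader might put the Section 8.1 gap at 10 weeks.** The 71-day figure ends treatment at the close of cycle 9 but starts scans from dose 9. With one anchor for both, the gap is 29 days.
- **The Cohort A gap on the CN/MET clock depends on the anchor.** If discontinuation means the end of cycle 9, the last scan is at 21 + 378 + 336 = day 735 to 42 + 378 + 336 = day 756, and that gap closes. The last-dose reading is the more natural one for completers, since Cohort A takes no study drug after Day 1 of cycle 9. The 29-day gap under Section 8.1 remains either way.
- **Windows and delays narrow the gap.** The latest restart with +14 days gives day 728; a ninth dose also 3 days late (Section 6.1) gives 731. Section 5.1.2.2 counts doses administered, so withheld doses given later move the last scan later.
- **Section 7.1.2 continues imaging to progression or end of study.** It refers back to the same schedule, however, and sets no landmark scan.
- **No censoring rule is stated.** Section 8.4.3 names Kaplan-Meier only for the medians, so an empty risk set is a consequence of the usual convention, not something the plan prescribes. Section 8.4.1 also calls these endpoints exploratory, although Sections 2.2.2 and 8.1 list them as secondary.

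These points limit the scope and size of the problem. They do not place a scan at the landmark, and they do not reconcile the two origins.

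**Conclusion.** The point holds for R0/R1 subjects who complete nine cycles on schedule. Their last planned scan is at least 29 days before the Section 8.1 time point in Cohorts A and B (15 days with the wider window). In Cohort A, counting follow-up from the last pembrolizumab dose, it is nominally 16 to 37 days before 2 years from CN/MET. Cohort B subjects still on axitinib reach the CN/MET landmark. A Cohort B subject who has stopped axitinib permanently and continues pembrolizumab alone, as Section 5.1.2.2 allows, follows the Cohort A timing.

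The assumptions are no dose delays, scans on their nominal day unless a window is stated, and week 48 as the last scan inside 12 months. The shortfall is smaller than the 12-week scan interval, so the effect on the estimate is likely modest. In Cohort A, the CN/MET rate would in effect be read at 693/730 × 24 = 22.8 to 714/730 × 24 = 23.5 months. The conflict between Sections 8.1 and 8.4.3 does not depend on these assumptions. This should be corrected, but it does not affect the primary endpoint.

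**What to change.** 1. Choose one time origin for the 1- and 2-year rates and use it in both Sections 8.1 and 8.4.3. If the origin is CN/MET, state a separate origin for subjects who have no surgery, such as metastatic subjects with a preoperative CR.
2. For nine-cycle completers, place the fourth follow-up scan at or after the 2-year landmark, with a stated window, and reconcile the ±14-day and ±7-day windows. Subjects on 18 cycles need no change on the CN/MET clock.
3. Extend the 12-month follow-up cap to fit. On the CN/MET clock the earliest restarts need 730 − 722 = 8 days, plus the chosen window. On the Section 8.1 clock with a single anchor, the landmark is day 365 itself, so only the window is added.
4. State what counts as the end of treatment for a completer, and the censoring rule.

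If the schedule is to stay, restate the endpoint as the rate at the last scheduled scan.

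The cost is one scan a few weeks later and a slightly longer follow-up period, with no additional scan. In Cohort A on the CN/MET clock, the interval between the third and fourth follow-up scans grows from 84 days to between 84 + 16 = 100 and 84 + 37 = 121 days, so a progression in that interval could be dated somewhat later.
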